### **Study Population- Marshallese Pregnant Women**

Participants must be female, age 18 or older, pregnant, who are self-reported Marshallese. Up to 100 women and up to 100 infants born to these women will be recruited through a bilingual community health worker and through our relationships with community organizations, specifically the Marshallese Education Initiative (MEI), Arkansas Coalition of Marshallese (ACOM), Marshallese pastors, and other community contacts developed through prior CBPR fieldwork.

# Inclusion Criteria

- Female
- 18 years of age or older
- Pregnant
- Self-reported Marshallese

### **Exclusion Criteria**

• Not Self-reported Marshallese

 Version #:10
 Page 8

 Date: 20250403
 IRB#261186

Maternal and Infant Health Outcomes of Marshallese in Arkansas

PI: [name]

Institution: University of Arkansas for Medical Sciences Northwest Campus

Under 18 years of age

Not pregnant

## Study Population-Clinical Staff and Marshallese Stakeholders

Participants must be age 18 or older, clinical staff and/or Marshallese stakeholders who participated in the implementation of a group prenatal program for Marshallese pregnant women.

### Inclusion Criteria

- 18 years of age or older
- Self-reported as clinical staff and/or Marshallese stakeholders who participated in the implementation of a group prenatal program for Marshallese pregnant women.

#### **Exclusion Criteria**

- Not self-reported as clinical staff and/or Marshallese stakeholders who
  participated in the implementation of a group prenatal program for Marshallese
  women.
- Under 18 years of age

# **Risks and Benefits**

There is no direct benefit, but what we learn may help other people in the future. Potential risks to study participants are minimal. There is a potential risk for loss of confidentiality. Potential risks to study participants by allowing access to information related to bills for healthcare services from the Arkansas All-Payer Claims Database are minimal. Measures to protect the confidentiality of study participants will be implemented as described in the Data Handling and Recordkeeping section.

### **Data Handling and Recordkeeping**

The principal investigator will carefully monitor study procedures to protect the safety of research subjects, the quality of the data and the integrity of the study. All study subject material will be assigned a unique identifying code or number. The key to the code will be kept in a locked file cabinet in a locked file room in the Office of Community Health and Research. Only the principal investigator and the study coordinator will have access to the code and information that identifies the subject in this study. At the conclusion of the study, the data will be permanently de-identified.

The study will comply with UAMS Admin Guide Policy 3.2.01 – research data, reports and analyses be retained for seven years after final reporting or publication of a project, or longer if required by a sponsor or regulation.

 Version #:10
 Page 9

 Date: 20250403
 IRB#261186

Maternal and Infant Health Outcomes of Marshallese in Arkansas

PI: [name]

Institution: University of Arkansas for Medical Sciences Northwest Campus

### **Data Analysis**

### Data collection and analysis for Aim 2:

A mixed-methods design will be used to determine the feasibility of Kōmmour Prenatal to improve adherence to recommended prenatal care visits and prenatal care satisfaction. After consent, and prior to the first focus group, participants will be asked to complete a survey. The survey may be completed in person or electronically via a link to REDCap. After participants have completed the survey, we will begin the focus group. Within the focus group, participants will be reminded to not disclose the identity of others who are participating or any information discussed. Focus groups will take place in a private room of a community-based organization- e.g. Jones center, hospital, UAMS-NW, local community church, or remotely using phone or a secure technology such as Zoom or Skype.

After the participants have provided consent and completed their first survey and focus group, participants will begin a series of up to 10 group prenatal sessions (Kōmmour Prenatal).

At third trimester participants will be asked to participate in an additional survey and focus group focused on their experiences in this intervention. Consistent with the first focus group, participants will be reminded to not disclose the identity of others who are participating or any information discussed. Focus groups will take place in a private room of a community-based organization- e.g. Jones center, hospital, UAMS-NW, local community church, or remotely using phone or a secure technology such as Zoom or Skype.

### Data collection for Aim 3:

A systematic medical chart review will be used to document the primary outcome of GWG and secondary outcomes of: breastfeeding initiation; birthweight of infant, preeclampsia; primary cesarean birth; and GDM from women enrolled in Kōmmour Prenatal and those in individualized care. Medical chart review data for the up to 100 pregnant Marshallese women who received individualized prenatal care will be from participants in studies previously approved by the UAMS IRB where the participants agreed to their data being used in related studies. Birth record data and the linkage to ADH data will be used to assess maternal and infant health outcomes. It is necessary to use both medical birth record and de-identified data through ADH to receive disaggregated data to identify matching covariates for the analyses. These variables will include maternal age, parity, and sociodemographic variables. Propensity scores will be estimated using the variables available for both the Centering Pregnancy participants and the participants in [name] cohort study. Each Centering Pregnancy participant will be propensity score matched without replacement with a participant in

Version #:10 Page 10 Date: 20250403 IRB#261186

Maternal and Infant Health Outcomes of Marshallese in Arkansas

PI: [name]

Institution: University of Arkansas for Medical Sciences Northwest Campus

the cohort study using a nearest neighbor algorithm. Success of matching will be assessed by comparing covariate balance between groups using both standardized differences in covariate means and graphical displays of group differences. Logistic regression will be used to test for differences in the outcomes between the Centering Parenting and the comparison group. PASS 2020 was used for statistical power analyses. The primary analysis for Aim 3 will be a logistic regression with intervention status predicting a binary outcome.

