## **Study Timeline**

Study initiation is planned for January 2021 with a duration of five years (60 months). Focus group guides and survey adaptation will take place in months 1-3. Enrollment will take place in months 4-16. Participants will attend up to 10 group prenatal sessions. The last participant enrolled will have time for final data collection prior to the end of the study at 60 months.

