# List of variables that may be collected from the Arkansas Department of Health:

Vital Statistics - Birth

Date of Birth (Infant)--Month

Date of Birth (Infant)—Day

Place Where Birth Occurred (type of place or institution)

Mother Married?-- At Conception, at Birth or any Time in Between

Date of First Prenatal Care Visit-Month

Total Number of Prenatal Care Visits

Mother's Height--Feet

Mother's Height-Inches

Mother's Weight at Delivery (in whole pounds)

Previous Live Births Now Living

Risk Factors--Prepregnancy Diabetes Risk Factors--Gestational Diabetes

Risk Factors--Prepregnancy Hypertension

Risk Factors--Gestational Hypertension

Risk Factors--Previous Preterm Births

Risk Factors--Poor Pregnancy Outcomes

Risk Factors--Infertility Treatment

Risk Factors--Previous Cesarean

Characteristics of Labor & Delivery--Meconium Staining

Characteristics of Labor & Delivery--Fetal Intolerance

Characteristics of Labor & Delivery--Anesthesia

Method of Delivery--Attempted Forceps (NCHS DELETED THIS ITEM EFFECTIVE 2011)

Method of Delivery--Attempted Vacuum (NCHS DELETED THIS ITEM EFFECTIVE 2011)

Method of Delivery--Route and Method of Delivery

Version #:10 Page 18 Date: 20250403 IRB#261186

Maternal and Infant Health Outcomes of Marshallese in Arkansas

PI: [name]

Institution: University of Arkansas for Medical Sciences Northwest Campus

Obstetric Estimation of Gestation

Congenital Anomalies of the Newborn--Down Syndrome

Congenital Anomalies of the Newborn--Suspected Chromosomal disorder

Congenital Anomalies of the Newborn—Hypospadias

Was Infant Transferred Within 24 Hours of Delivery? Is Infant Living at Time of Report?

Is Infant Being Breastfed? (RECOMMENDED CHANGE TO "AT DISCHARGE" EFFECTIVE 2004)

Risk Factors--Hypertension Eclampsia (RECOMMENDED ADDITION EFFECTIVE 2004)

Mother's Age (Calculated)

Mother's Race - Specify

State of Birth FIPS Code (Required)

Verification of height (Mother)

Verification of pre-pregnancy weight

Did mother smoke three months before or during pregnancy? Prenatal care?

Verification of number of prenatal care visits Obstetric procedures - none selected Medical risk factors - none selected Infection present - none selected

Maternal morbidity - none selected

Characteristics of labor - none selected

Mother transferred in for delivery?

Onset of labor - none selected Weight units

Pounds

Ounces

Plurality

Infant abnormal conditions - none selected

 Version #:10
 Page 19

 Date: 20250403
 IRB#261186

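### Aim 3 gives no delivery period for its comparison group and makes no use of delivery date, so any period difference between the groups is counted as an effect of Kōmmour Prenatal

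*Combined protocol and SAP*

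**What the plan says.** The Specific Aims set up Aim 3 as a comparison of effectiveness, with gestational weight gain (GWG) as primary outcome and five secondary outcomes expected to improve. The population and schedule sections describe recruitment of the Kōmmour Prenatal women only. Under Data collection for Aim 3, chart data for the individualized-care group "will be from participants in studies previously approved by the UAMS IRB where the participants agreed to their data being used in related studies".

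The same section describes the adjustment. Of the matching covariates it says: "These variables will include maternal age, parity, and sociodemographic variables". It adds: "Propensity scores will be estimated using the variables available for both the Centering Pregnancy participants and the participants in" a named cohort study. Each intervention woman is then matched without replacement to a woman in "the cohort study using a nearest neighbor algorithm". Balance is judged by standardized differences and graphs. The analysis is stated as: "The primary analysis for Aim 3 will be a logistic regression with intervention status predicting a binary outcome".

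On timing, the Study Timeline gives a planned start in January 2021, a 60-month duration, and "Enrollment will take place in months 4-16". No date or period is given for the comparison cohort.

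Two places bear on whether delivery date is available. Study Design and Procedures lists infant date of birth among the items abstracted from medical records. Appendix 1, the Arkansas Department of Health (ADH) list, has "Date of Birth (Infant)--Month" and the day, but no year.

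**The concern.** With no concurrently recruited control group, the comparison is sound only if the two sets of pregnancies are alike in everything but the type of prenatal care. Calendar period is one way they can differ. Gestational diabetes testing, cesarean practice, breastfeeding support, record coding and weight gain itself can all change over a few years. Matching on age, parity and sociodemographic variables does not remove such a change, and a model with intervention status as its only named predictor cannot either.

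The credibility of every Aim 3 outcome is at stake. A favorable trend could produce the expected improvement without any effect of the program, and an unfavorable one could hide a real benefit. The bias is systematic, so recruiting more women does not reduce it.

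**Working it through.** **1. Is calendar time handled anywhere?** I looked for each way in which the plan could deal with it.

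- Comparator delivery or enrolment dates: not stated.
- Required overlap with the intervention pregnancies: none. If month 1 is January 2021, intervention enrolment runs from April 2021 (month 4) to April 2022 (month 16). There is nothing to set against this on the comparator side.
- Named matching covariates: maternal age, parity, sociodemographics. Delivery date is not among them.
- Matching algorithm: nearest neighbor without replacement, with no date window.
- Balance check: on covariates, so it covers date only if date is one of them.
- Primary model: intervention status is the only predictor named.
- Sensitivity analysis for period: none.

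**2. Could the open rule on available variables cover it?** The score may use any variable held for both groups, which could include delivery date. That helps only where the periods overlap. If every comparator delivered before every intervention woman, delivery date predicts group perfectly. No comparator then has a similar date, and neither a propensity score nor a regression term can separate period from intervention.

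**3. How large could the effect be?** The plan names power software for Aim 3 but gives no alpha, power, effect size or event rate, so there is no figure to reproduce. What follows is an illustration.

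*Assumptions, none from the documents except the group size (the stated maximum):* n = 100 per group, comparator rate p0 = 0.50, no true effect, intervention-period rate p1 = p0 + d from drift d alone, no overlap in time, independent women, two-sided 5% test of two proportions.

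*Formulas:* SE = √{[p0(1−p0) + p1(1−p1)]/n}. Rejection probability = Φ(d/SE − 1.96) + Φ(−d/SE − 1.96). Odds ratio = [p1/(1−p1)]/[p0/(1−p0)].

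- d = 0.05: SE = √(0.4975/100) = 0.0705; d/SE = 0.709; Φ(−1.251) + Φ(−2.669) = 0.109. Odds ratio = 0.55/0.45 = 1.22.
- d = 0.10: SE = √(0.4900/100) = 0.0700; d/SE = 1.429; Φ(−0.531) + Φ(−3.389) = 0.298. Odds ratio = 0.60/0.40 = 1.50.
- d = 0.15: SE = √(0.4775/100) = 0.0691; d/SE = 2.171; Φ(0.211) plus a negligible second term = 0.583. Odds ratio = 0.65/0.35 = 1.86.

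With d = 0 the result is 0.050.

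*Sensitivity to the assumptions.* Pooling the variance in the test statistic gives 0.109, 0.294 and 0.575 for the same three cases. With that pooled version and base rates from 30% to 70%:

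| Drift | 100 per group | 50 per group |
|---|---|---|
| 5 points | 11% to 12% | 8% to 9% |
| 10 points | 29% to 37% | 17% to 21% |
| 15 points | 57% to 72% | 32% to 43% |

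The false-positive rate rises with sample size because the bias stays equal to the drift while the standard error falls.

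**The case against.** A reader might infer from the source of the comparators that they are historical controls. The documents do not support that. The phrase about prior approval describes ethics review of the source studies, not when the pregnancies took place, and the cohort may partly or wholly overlap with Kōmmour Prenatal. The cohort's name has been removed from the public text, and a reader who knows the study may know its dates. This objection stands: non-concurrence is possible but unproven. It does not close the gap, because a name is neither a stated delivery period nor a requirement of overlap.

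A reader might also infer from Appendix 1 that year of birth is unavailable. That too goes too far. Infant date of birth is already on the chart-abstraction list, and Aim 3 outcomes come from chart review in both groups. The list is written for this study's own participants, so the date still has to be secured for the comparators. The missing ADH year is a minor point.

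The illustration can fairly be called generic: nothing in the documents suggests a drift of any particular size, and any unmeasured confounder of the same strength would give the same numbers. Finally, Study Design and Procedures calls the purpose feasibility and preliminary effectiveness, for which a matched external cohort is a common choice. That argues for a modest remedy and careful wording, not for leaving period out, since Aim 3 still compares effectiveness and runs a test.

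**Conclusion.** The point holds in conditional form. The plan neither states the comparators' delivery period nor requires overlap, and delivery date appears in neither the named matching set, the stated model nor any sensitivity analysis. Any difference in delivery period is therefore left in the Aim 3 estimate for the primary outcome and all secondary outcomes. The documents do not show that the cohorts fail to overlap, that a drift occurred, or how large it would be.

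The figures of about 11%, 30% and 58% false positives for drifts of 5, 10 and 15 points rest on the assumed 50% base rate, 100 women per group, complete separation in time and no true effect. They show how sensitive the comparison is and do not estimate its actual error. The matter should be settled before the Aim 3 analysis is run.

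**What to change.** In Data collection for Aim 3:

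1. State the comparison cohort's delivery dates beside those of the Kōmmour Prenatal women.
2. Where the dates overlap, add delivery date to the matching, through the propensity score or a stated window, and to the balance check. Infant date of birth is already listed for chart abstraction; obtain it for the comparators as well.
3. Report a sensitivity analysis restricted to overlapping delivery dates.
4. If there is no overlap, word the Aim 3 conclusion as a historical-control comparison that cannot separate the intervention from period.

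An ADH-based estimate of the change between periods is optional. It needs a population extract of Marshallese births with year of birth. The protocol does not clearly plan one: it describes ADH data as linked to study participants and as a source of matching covariates. As Appendix 1 stands, it would not cover GWG or preeclampsia, so it could not protect the primary outcome.

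The cost is protocol wording, one date field for the comparators and one extra analysis. Some matches may be lost and the estimate may be less precise; how much depends on the overlap, which the documents do not give.

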To reduce the participant burden, information regarding birth and/or death outcomes and other variables may be collected up to 7 years post-delivery and linked to the participant and her child(ren) from one of the following sources: (1) the mother's electronic medical record at UAMS; (2) the Arkansas Department of Health (ADH) birth and/or death records; (3) the Arkansas All Payers Claims Database (APCD); or (4) via a release of information signed by the mother for babies delivered outside of UAMS. The consent document will include consent for each of these sources. Data collected from these sources may include: general contact and background information about (such as name, address, and telephone number), living situation, income, educational background, maternal medical history, and birth outcomes (gestational age, birth weight, complications, etc). A complete list of data that may be collected from the ADH is attached to this protocol in Appendix 1. Participants will be asked to acknowledge their understanding of this data collection at the time of consent. Participants will have the opportunity to choose if they wish to be re-contacted for future research at the time of consent.

In addition, data from this study will be linked to vital birth record information from the Arkansas Department of Health. Participants will be asked to acknowledge their understanding of this data collection at the time of consent. Data collected from the Arkansas Department of Health may include, but is not limited to: demographic and socioeconomic information, maternal medical history, and birth outcomes (gestational age, birth weight, complications, etc). Because data from birth records is aggregated, data from the Arkansas Department of Health will provide disaggregated data so that covariates (demographic and socioeconomic variables) can be used in the analyses.

Participants will have the opportunity to choose if they wish to be re-contacted for future research at the time of consent.

We will collect the following information via medical record abstraction:

For Marshallese participants who are pregnant:

- date of first prenatal care visit
- number of prenatal care visits
- fasting glucose
- weight and height
- blood pressure
- gestational weeks at delivery
- complications

 Version #:10
 Page 6

 Date: 20250403
 IRB#261186

Maternal and Infant Health Outcomes of Marshallese in Arkansas

PI: [name]

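### Aim 3 does not commit baseline BMI or pre-pregnancy history to the propensity score, and its primary logistic model names no covariate beyond intervention status.

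*Combined protocol and SAP*

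**What the plan says.** The section on data collection for Aim 3 sets out a chart review of gestational weight gain (GWG, primary) and of breastfeeding initiation, birthweight, preeclampsia, primary cesarean and gestational diabetes. It covers women in Kōmmour Prenatal "and those in individualized care". The comparison women come from earlier studies, with up to 100 women per group (also in Specific Aims).

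Control of selection rests on these statements in that section:

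- Named matching covariates: "These variables will include maternal age, parity, and sociodemographic variables".
- Rule for the score: "Propensity scores will be estimated using the variables available for both the Centering Pregnancy participants and the participants in" a prior cohort study.
- Matching: each intervention participant is paired with one cohort participant by nearest neighbor, without replacement. No caliper is stated.
- Check: "Success of matching will be assessed by comparing covariate balance between groups using both standardized differences in covariate means", together with graphs.
- Model: "The primary analysis for Aim 3 will be a logistic regression with intervention status predicting a binary outcome".

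Study Design and Procedures describes the health department linkage as a source of "demographic and socioeconomic information, maternal medical history, and birth outcomes", but gives the purpose of the disaggregated data as "so that covariates (demographic and socioeconomic variables) can be used in the analyses". The chart abstraction list for pregnant participants includes "weight and height". Appendix 1 lists items that may be collected, among them pre-pregnancy diabetes and hypertension, previous preterm births, maternal height and a verification item for pre-pregnancy weight.

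**The concern.** In a non-randomised comparison, the covariates in the score and the outcome model are the only protection against selection. Baseline BMI and pre-existing diabetes or hypertension are plausible determinants both of who joins a group program and of GWG, gestational diabetes, preeclampsia and birthweight. The plan names none of them, although its own data sources appear able to supply them for the intervention group. If they remain unbalanced after matching on age, parity and sociodemographic variables, a model with intervention status alone attributes the difference to the program. An open rule also leaves the covariate set to be chosen once the comparison data are in hand, with no required minimum.

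**Working it through.** **1. Reading the text.** The plan gives no alpha, power, effect size or event rate for Aim 3, only the name of the power software, so there is no figure to reproduce. The statements compare as follows:

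| Item | Collected or listed? | Named for score? | Named in primary model? |
|---|---|---|---|
| Maternal age, parity, sociodemographics | Yes | Yes | No |
| Weight and height (hence BMI) | Yes, study participants | No | No |
| Pre-pregnancy diabetes, hypertension, previous preterm birth | May be collected | No | No |

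Parity is the only element of obstetric history that is named. The availability rule permits the other rows and does not require them. What the comparison cohort holds is not described, but GWG cannot be charted in that group without some starting weight.

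**2. What confounding could do (illustration only).** All inputs are assumed except the 15% base rate, which is the low-birthweight proportion in Background and Rationale. Assumptions: no true effect; 100 per group; one omitted covariate x, distributed N(0,1) in one group and N(d,1) in the other, where d is the imbalance left after matching. The model is P(Y=1) = expit(a + log(OR)·x), with a solved for the base rate. Marginal rates come from 80-point Gauss-Hermite quadrature. Rejection by the two-sided 5% Wald test of the unadjusted log odds ratio is found by exact enumeration of both binomials. No matching is modelled.

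| Covariate OR per SD, d | Spurious OR, 15% base | Rejection | Spurious OR, 50% base (assumed) | Rejection |
|---|---|---|---|---|
| no confounding | 1.00 | 4.5% | 1.00 | 5.6% |
| 1.5, 0.1 | 1.04 | 4.6% | 1.04 | 5.8% |
| 2.5, 0.1 | 1.09 | 5.0% | 1.08 | 6.5% |
| 1.5, 0.2 | 1.08 | 5.0% | 1.08 | 6.5% |
| 2.0, 0.3 | 1.22 | 7.4% | 1.21 | 11.0% |
| 2.5, 0.5 | 1.50 | 18.8% | 1.48 | 29.0% |

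With x added to the outcome model, simulated rejection (20,000 trials per cell) was 4.5% to 5.0%, with a median adjusted odds ratio of 1.00. That assumes one confounder, measured without error and correctly modelled. None of this sizes the effect on GWG, for which the plan gives no binary definition or event rate.

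**3. What matching can do at this pool size.** If 100 intervention women are matched 1:1 without replacement to a pool of 100, with no caliper, every pool member is used. The matched comparison group is then the whole pool and balance is unchanged, whatever is in the score. In simulation, an initial difference of 0.3 SD on the matched variable stayed at about 0.3 with a pool of 100. It fell to about 0.05 with 150 and 0.02 with 200 (both pool sizes assumed). With the smallest pool, only adjustment in the outcome model removes imbalance, and that includes imbalance in the covariates already named.

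**The case against.** The strongest reply is that the availability rule, read broadly, already brings BMI and history into the score if both cohorts hold them, so little is missing. That holds to this extent: the plan does not exclude them, and a reader who infers that it does goes beyond the text. But permission is not commitment. The only wording that describes the covariates, in two sections, stays with age, parity and demographic or socioeconomic variables.

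A reader might also infer that the plan would match on post-treatment variables, because Appendix 1 mixes history with delivery weight, visit count and gestational diabetes. The documents do not support that. Every covariate the plan names is a baseline variable, no text proposes matching on later ones, and Appendix 1 lists what may be collected and carries a placeholder comment. A timing limit is worth one clarifying sentence and is not the correction of a planned error.

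A third inference is that the balance check is defective because it states no threshold or remedy. At 100 per group the SD of a standardized difference is sqrt(2/100) = 0.141, so even randomised groups would exceed 0.1 for 48% of covariates and 0.25 for 7.7%. A threshold alone would settle little, and I do not press this.

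It is also fair to say that a treatment-only model after matching is an accepted analysis, that the study is framed as preliminary, and that the larger rejection rates rest on inputs no document supports. These limit the weight of the point. They do not answer it where matching cannot improve balance.

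**Conclusion.** The point holds as a gap in commitment. Neither the named matching list nor the primary model requires baseline BMI or pre-pregnancy history, in a non-randomised comparison whose primary outcome is weight gain. The bias is of unknown size and may be zero. At a residual imbalance of 0.1 SD it is immaterial in the illustration, and the 19% to 29% figures need both a strong covariate and an imbalance of 0.5 SD. It would be wrong to conclude that the comparison fails or is known to be biased. The case for outcome adjustment depends on pool size: it is strongest if the phrase up to 100 describes the whole pool, and weaker if many more women are available. The change should be made, but it is not essential to the study's feasibility aims. Confidence is medium, because the comparison cohort's data are not described.

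**What to change.** Before matching:

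- Add baseline BMI to the named propensity variables: pre-pregnancy BMI, or first-visit BMI together with gestational age at that visit, since a late first weight already contains gain.
- Add pre-pregnancy diabetes, pre-pregnancy hypertension and previous preterm birth where both cohorts hold them. Smoking is better left off unless a cleaner item exists, because the only one listed spans the time before or during pregnancy.
- As a clarification, limit the score to variables fixed before group care, with baseline worded so that it applies equally to comparison women (pre-pregnancy or entry to prenatal care).
- State the size of the comparison pool.

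In the primary analysis, adjust the logistic regression for baseline BMI and the few named matching variables. State that the odds ratio is then conditional, or standardise it to a marginal estimate.

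The cost is protocol wording and a check of what the comparison cohort holds; some variables may be missing there. The list must stay short. At a 15% event rate, 200 women give about 200 × 0.15 = 30 events, and each added covariate makes close matches harder to find. The adjusted odds ratio is not directly comparable with the unadjusted one unless standardised.
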